6.3.3. Blinding of the Sponsor

Those study team members who are involved in ensuring that protocol requirements for study intervention preparation, handling, allocation, and administration are fulfilled at the site will be unblinded for the duration of the study (eg, unblinded study manager, unblinded clinical research associate). An unblinded clinician who is not a direct member of the study team will review unblinded protocol deviations. All other study team members will remain blinded to the vaccine assigned/received through and including Visit 5 (1 month after Vaccination 2). All laboratory testing personnel performing serology assays will remain blinded to vaccine assigned/received and to visit number throughout the study.

6.3.4. Breaking the Blind

At the initiation of the study, the study site will be instructed on the method for breaking the blind. The method will be either a manual or an electronic process. Blinding codes should only be broken in emergency situations for reasons of participant safety.

In case of an emergency, when knowledge of the study intervention assignment is required for the medical management of an individual participant, it may be unblinded. The investigator must notify a member of the study team immediately after determining that it is necessary to unblind the assignment. The investigator must also indicate in source documents that the blind was broken and provide the date and reason for breaking the blind. Any AE or SAE associated with breaking the blind must be recorded and reported as specified in this protocol.

6.3.5. Planned Unblinding

Pfizer will release unblinding information to the investigators after all participants have completed the blood draw at Visit 5 (1 month after the second dose of MenABCWY in Group 1 [0- and 12-month schedule] or 1 month after placebo in Group 2 [0- and 36-month schedule]). Additional information is included in the ISF.

The second dose of MenABCWY in Group 2 (0- and 36-month schedule) will be administered in an open-label manner.

6.4. Study Intervention Compliance

All doses of study intervention will be administered by the appropriately designated study staff at the investigator site.

6.5. Concomitant Therapy

The name and date of administration of any nonstudy vaccine (or allergen immunotherapy) given from the signing of the ICD up to approximately 6 months after Vaccinations 1 and 2, within approximately 1 month after Vaccination 3 (Group 2 only), and within 28 days before administration of study intervention at Visit 4 and Visit 9 will be recorded on the CRF. The name and date of administration for any nonstudy meningococcal vaccine received, which is exclusionary, will be collected from the signing of the ICD up to the end of study participation.

The name, start and stop dates, and route of administration for concomitant medications (prescription and nonprescription) used to treat an AE from the signing of the ICD to the final visit will be recorded in the CRF.

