1.2. Schema

Group 1 (0- and 12-Month Schedule)							
	Vaccination 1	1 Month Post–Vaccination 1 Blood Draw	Safety Telephone Contact 1	Vaccination 2	1 Month Post–Vaccination 2 Blood Draw	12-Month Antibody Persistence Visit	24-Month Antibody Persistence Visit
Approximate Month	0	1	6	12	13	24	36
Visit Number	1	2	3	4	5	6	7 ^a
Group 1 (n=150)	MenABCWY			MenABCWY			
Blood draw	25 mL	25 mL			25 mL	25 mL	25 mL

a. Visits 8, 9, and 10 will not be conducted for Group 1 participants.

Group 2 (0- and 36-Month Schedule)								
	Vaccination 1	1 Month Post–Vaccination 1 Blood Draw	Safety Telephone Contact 1	Vaccination 2	1 Month Post–Vaccination 2 Blood Draw	Safety Telephone Contact 2	Vaccination 3	1 Month Post–Vaccination 3 Blood Draw
Approximate Month	0	1	6	12	13	24	36	37
Visit Number	1	2	3	4	5 ^a	8 ^b	9	10
Group 2 (n=150)	MenABCWY			Saline			MenABCWY	
Blood draw	25 mL	25 mL			25 mL			25 mL

a. Visits 6 and 7 will not be conducted for Group 2 participants.

b. Visit 8 will be scheduled as an in-person visit to maintain the blind and converted to a telephone visit once unblinding has occurred.

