1.3. Schedule of Activities

The SoA table provides an overview of the protocol visits and procedures. Refer to the **STUDY ASSESSMENTS AND PROCEDURES** section of the protocol for detailed information on each procedure and assessment required for compliance with the protocol.

The investigator may schedule visits (unplanned visits) in addition to those listed in the SoA table, in order to conduct evaluations or assessments required to protect the well-being of the participant.

Group 1 (0- and 12-Month Schedule)							
Visit Identifier Abbreviations used in this table may be found in Appendix 7	Visit 1	Visit 2	Visit 3	Visit 4	Visit 5	Visit 6	Visit 7 ^a
Visit Description	Vaccination 1	1 Month Post– Vaccination 1 Blood Draw	Safety Telephone Contact 1	Vaccination 2	1 Month Post– Vaccination 2 Blood Draw	12-Month Antibody Persistence Visit	24-Month Antibody Persistence Visit
Approximate Month	0	1	6	12	13	24	36
Visit Window	Day 1	28 to 42 Days After Visit 1	168 to 196 Days After Visit 1	336 to 394 Days After Visit 1	28 to 42 Days After Visit 4	336 to 394 Days After Visit 4	700 to 756 Days After Visit 4
Informed consent	X						
Review eligibility criteria	X						
Demography	X						
Confirm continued eligibility ^b		X	X	X	X	X	X
Medical history	X						
Physical examination	X			X			
Record previous PRP-OMP vaccinations	X						
Urine pregnancy test for female participants (obtain results prior to vaccination)	X			X			
Oral temperature (prior to vaccination)	X			X			
Randomization	X						
Obtain blood sample (~25 mL)	X	X			X	X	X

Group 1 (0- and 12-Month Schedule)

Visit Identifier Abbreviations used in this table may be found in Appendix 7	Visit 1	Visit 2	Visit 3	Visit 4	Visit 5	Visit 6	Visit 7 ^a
Visit Description	Vaccination 1	1 Month Post– Vaccination 1 Blood Draw	Safety Telephone Contact 1	Vaccination 2	1 Month Post– Vaccination 2 Blood Draw	12-Month Antibody Persistence Visit	24-Month Antibody Persistence Visit
Approximate Month	0	1	6	12	13	24	36
Visit Window	Day 1	28 to 42 Days After Visit 1	168 to 196 Days After Visit 1	336 to 394 Days After Visit 1	28 to 42 Days After Visit 4	336 to 394 Days After Visit 4	700 to 756 Days After Visit 4
Study intervention administration and observation ^c	X			X			
Record nonstudy vaccinations ^d		X	X	X	X	X	
Provide the participant with a contact card	X						
Provide the participant with a memory aid		X			X		
Complete Study Visit/Telephone Contact AE Checklist ^e		X	X	X	X	X	X

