2.1. Study Rationale

In Study B1971057, an FIH and POC study for MenABCWY, 543 participants received MenABCWY on a 0- and 6-month schedule. Results from B1971057 indicated MenABCWY, when given on a 0- and 6-month schedule, is well tolerated with an acceptable safety profile and also provides a high degree of protective immune responses without interference among all 5 serogroup components tested. These results are comparable to Phase 2 and 3 bivalent rLP2086 studies, which demonstrate that by increasing the interval between 2 doses, immune responses are enhanced. Study B1971057 also demonstrated that 1 dose of MenACWY-TT (Nimenrix), as a component of MenABCWY, provides protective immune responses in a high proportion of those vaccinated, consistent with Phase 3 data supporting licensure of Nimenrix.

The aim of this Phase 2b descriptive study is to assess the potential utility of MenABCWY in the framework of current US meningococcal vaccination practices, which are based on ACIP recommendations. The ACIP recommends that children 11 to 12 years of age should receive a MenACWY conjugate vaccination with a booster dose at 16 years of age and that adolescents and young adults 16 to 23 years of age may be vaccinated with a 2- or 3-dose series MenB vaccine to provide short-term protection against most strains of serogroup B meningococcal disease. A single dose of MenACWY conjugate provides protection in early adolescence, but the second dose is required to extend that protection into late adolescence

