8.11.1.7. Visit 7, Month 36, (24 Months [700 to 756 Days] After Visit 4), 24-Month Antibody Persistence Visit

- Ensure that the participant continues to be eligible for the study and continues to comply with contraception requirements detailed in [Section 5](#).
- Ensure that the participant continues to meet none of the withdrawal criteria as described in [Section 7](#) and none of the temporary delay of blood draw criteria as described in [Section 5.5.2](#).
- Complete the Study Visit/Telephone Contact AE Checklist to:
 - Inquire whether the participant had any NDCMCs since the last visit. Inquire whether the participant had any of the following related to an AE since the last visit: hospitalizations, visits to other medical facilities, medication use, or missed days of school or work. Please refer to the ISF for additional details.
 - Inquire about neuroinflammatory and autoimmune conditions, such as transverse myelitis, uveitis, optic neuritis, and multiple sclerosis. Please refer to the ISF for additional details.
- Record AEs as described in [Section 8.3](#) and the [SoA](#).
- Review AEs that were ongoing since the previous visit, and record their end dates or confirm that they are still continuing.
- Record concomitant medications used to treat AEs as described in [Section 6.5](#).
- Collect a blood sample (approximately 25 mL).
- Ask the parent(s)/legal guardian to contact the investigator about any AEs occurring during the 48-hour period after the blood draw.
- Ask the parent(s)/legal guardian to contact the investigator immediately if any significant illness or hospitalization occurs.
- Complete the source documents.
- Complete the CRFs.

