8.11.2.8. Visit 10, Month 37 (1 Month [28 to 42 Days] After Visit 9), 1-Month Post-Vaccination 3 Blood Draw

- Ensure that the participant continues to be eligible for the study and continues to comply with contraception requirements detailed in [Section 5](#).
- Ensure that the participant continues to meet none of the withdrawal criteria as described in [Section 7](#) and none of the temporary delay of blood draw criteria as described in [Section 5.5.2](#).
- Complete the Study Visit/Telephone Contact AE Checklist to:
 - Inquire whether the participant had any NDCMCs since the last visit. Inquire whether the participant had any of the following related to an AE since the last visit: hospitalizations, visits to other medical facilities, medication use, or missed days of school or work. Please refer to the ISF for additional details.
 - Inquire about neuroinflammatory and autoimmune conditions, such as transverse myelitis, uveitis, optic neuritis, and multiple sclerosis. Please refer to the ISF for additional details.
- Record AEs as described in [Section 8.3](#) and the [SoA](#).
- Review AEs that were ongoing since the previous visit, and record their end dates or confirm that they are still continuing.
- Record concomitant medications used to treat AEs as described in [Section 6.5](#).
- Record nonstudy vaccinations as described in [Section 6.5](#).
- Collect a blood sample (approximately 25 mL).
- Ask the parent(s)/legal guardian to contact the investigator immediately if any significant illness or hospitalization occurs.
- Complete the source documents.
- Complete the CRFs.

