## **3.6. Study Conduct**

### **3.6.1. Nonstudy Vaccines and Concomitant Medications**

The name and date of administration of any nonstudy vaccine (or allergen immunotherapy) given from the signing of the ICD up to approximately 6 months after Vaccinations 1 and 2, within approximately 1 month after Vaccination 3 (Group 2 only), and within 28 days before administration of study intervention at Visit 4 and Visit 9 will be recorded on the CRF. The name and date of administration for any nonstudy meningococcal vaccine received will be collected from the signing of the ICD up to the end of study participation.

Concomitant vaccines and medications permitted during the study include:

- Nonstudy vaccines used in the event of a disease outbreak or pandemic are allowed. In such situations, effort should be made to appropriately plan the administration of study intervention around dosing of the pandemic vaccine.
- Nonstudy vaccines (other than any meningococcal vaccines) that are part of recommended immunization schedules are allowed anytime during the study but should not be administered within 14 days (for nonlive vaccines) and 28 days (for live vaccines) before or after administration of study intervention.
- Antipyretic and other pain medication to treat symptoms following administration of study intervention is permitted.
- A local anesthetic may be used at the site of the blood draw.
- Topical antibiotics are permitted.
- Topical and inhaled corticosteroids are permitted.
- Hormonal contraceptives that meet the requirements of this study are allowed to be used in participants who are WOCBP.

The name, start and stop dates, and route of administration for concomitant medications (prescription and nonprescription) used to treat AEs from the signing of the ICD through the final visit will be recorded in the CRF.

Treatments will be categorized according to the current version (at the time of reporting) of the WHO Drug Dictionary.

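### Group 1's last visit (Visit 7) has no scheduled step to ask about or record nonstudy meningococcal vaccine, although protocol 6.5 and SAP 3.6.1 require collection to the end of participation

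*Protocol*

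**What the plan says.** Protocol 6.5 sets the collection period: "any nonstudy meningococcal vaccine received, which is exclusionary, will be collected from the signing of the ICD up to the end of study participation". SAP 3.6.1 carries the same duty: "any nonstudy meningococcal vaccine received will be collected from the signing of the ICD up to the end of study participation". Protocol 6.5.1 lists these vaccines as prohibited.

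The visit schedule does not carry this through for Group 1. In protocol 1.3 the row "Record nonstudy vaccinations" is marked at Visits 2 to 6 and blank at Visit 7, and the copy in SAP 2.2.1 shows the same pattern. The procedure list under "8.11.1.7. Visit 7, Month 36, (24 Months [700 to 756 Days] After Visit 4), 24-Month Antibody Persistence Visit" passes from concomitant medications straight to the blood sample. No later contact can pick the data up: "Visits 8, 9, and 10 will not be conducted for Group 1 participants".

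The step does appear at Group 1's preceding visit (Visit 6, section 8.11.1.6) and at Group 2's last visit (Visit 10, section 8.11.2.8: "Record nonstudy vaccinations as described in" Section 6.5).

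The Visit 7 titers feed the 24-month persistence percentages for MenB and ACWY (protocol 9.4.1; SAP 6.2.1.2 and 6.2.1.3), analysed in the post-Vaccination 2 evaluable population. For Group 1, that population screens for prohibited vaccines and important deviations through Visit 5 only (protocol 9.3; SAP 4).

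**The concern.** Protocol 8 makes adherence to the Schedule of Activities a requirement, so a compliant site has no prompt to ask about vaccines at Visit 7. Other Visit 7 items do not fill the gap. The AE checklist asks about AE-related care, newly diagnosed chronic conditions, missed days and autoimmune conditions. Protocol 8.2 excludes preventive-care visits from collection. Concomitant medications are recorded only when used to treat an AE.

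The timing makes this more than clerical. The schedule cited in protocol 2.1 gives MenACWY in early adolescence "with a booster dose at 16 years of age" and allows MenB vaccine from 16. An off-study dose before the Visit 7 draw would tend to raise that titer, which would then be reported as persistence of two MenABCWY doses. A MenACWY vaccine would affect only the ACWY results, and a MenB vaccine only the MenB results. The nonstudy-vaccine listing promised in SAP 6.5.4 would also look complete when it might not be.

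**Working it through.** **Length of the unprompted interval** (windows from protocol 1.3, counted from Visit 4; the extension is in 8.11.1.6)

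- Visit 6: day 336 to 394, extendable by up to 60 days to 394 + 60 = 454. Visit 7: day 700 to 756.
- Longest gap: 756 − 336 = 420 days.
- Shortest gap: 700 − 394 = 306 days, or 700 − 454 = 246 days with the full extension.

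**Age during the interval** (entry age ≥11 to <15, protocol 5.1)

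- Nominal months: entrants aged 13 turn 16 between Months 24 and 36; entrants aged 14 are already 16 or older throughout.
- Earliest windows: Visit 7 falls 336 + 700 = 1036 days after Visit 1, or 1036/365.25 = 2.84 years. Someone enrolled on a 13th birthday would be 15.84 and would not reach 16.
- Latest windows: 394 + 756 = 1150 days, or 3.15 years. Entrants aged 11 do not reach 16; entrants aged 12 do so only if enrolled shortly before turning 13.
- The documents give no age mix, so the exposed share of Group 1 cannot be computed.

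**Planned precision** (protocol Table 4, 120 evaluable per group). Clopper-Pearson half-widths at n = 120 come to 9.09, 8.53, 7.51 and 5.77 points at 60%, 70%, 80% and 90%. These reproduce the stated 9.1, 8.5, 7.5 and 5.8.

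**Possible bias.** Let f be the share of Visit 7 results taken after an unelicited vaccination, p_vax the percentage of those at or above LLOQ, and p_true the percentage had they not been vaccinated. Then bias = f × (p_vax − p_true). With p_vax = 95% (assumed):

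| p_true (assumed) | f = 5% | f = 10% | f = 20% | Table 4 half-width |
|---|---|---|---|---|
| 60% | 0.05 × 35 = +1.75, shown as +1.8 | +3.5 | +7.0 | 9.1 |
| 80% | 0.05 × 15 = +0.75 | +1.5 | +3.0 | 7.5 |
| 90% | 0.05 × 5 = +0.25 | +0.5 | +1.0 | 5.8 |

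As a partial guide to p_true for MenB, protocol 2.2.2.1 reports 57.5% to 82.8% at or above LLOQ up to 2 years after a Trumenba booster, a different setting. At f = 10% that range gives 0.10 × (95 − 57.5) = +3.75 down to 0.10 × (95 − 82.8) = +1.22 points.

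**The case against.** The strongest objection is that the missing step does not by itself create the bias, and adding it would not remove the bias. Under the written population rules, a vaccine fully recorded at Visit 7 would still leave the participant and the titer in the persistence summary, because the Group 1 screen stops at Visit 5. This stands, and the fix must include an analysis rule. It does not dispose of the point: without the record, no exclusion, sensitivity analysis or count of affected participants is possible.

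Second, a reader might infer that a vaccine given after Visit 6 necessarily goes unrecorded. The documents do not support that. The 6.5 duty stands whatever the schedule shows, and Visit 7 retains checks of continued eligibility (Section 5 includes never having had a meningococcal vaccine) and of withdrawal criteria. A vaccination could surface there or by spontaneous report. What is missing is a scheduled step to elicit and record name and date. The eligibility check is not treated as a substitute elsewhere, since Visits 6 and 10 carry both it and the recording step.

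Third, it would be tempting to take the protocol's US coverage figures (50.8% for at least two MenACWY doses, 17.2% for MenB) as guides to f. They describe US adolescents generally, not participants barred from these vaccines who have already had two MenABCWY doses. The true f may be small.

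Finally, this concerns one time point of secondary endpoints in a descriptive study with no hypothesis tests.

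**Conclusion.** The inconsistency is real and appears in three places: the protocol schedule, its SAP copy and section 8.11.1.7. It leaves 246 to 420 days before the 24-month draw without a scheduled vaccine check in Group 1 (306 to 420 if Visit 6 is not extended).

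The likely direction is upward, overstating 24-month persistence. The size is unknown: f, p_vax and p_true are all assumptions. Over the range shown, the bias runs from +0.25 to +7.0 points, below the planned half-width in every cell. The +7.0 needs both the lowest baseline and the highest f.

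Two further inferences fail. Not every entrant aged 13 to <15 must be 16 during the gap, as the earliest-window case shows. Nor are the primary endpoints touched: Group 1's immunogenicity endpoint is read at Visit 5, and Group 2's recording runs through Visit 10. The correction is worth making because it is cheap and the information is needed for any defensible handling of these titers.

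**What to change.** 1. **Collection.** Mark the nonstudy-vaccination row at Visit 7 in the Group 1 schedule (protocol 1.3 and SAP 2.2.1) and add the step to 8.11.1.7. Before the blood draw, ask about any nonstudy meningococcal vaccine since Visit 6 and record its name and date. For participants already past Visit 7, send a site query or check vaccination records before database lock. The documents do not show how many have passed it.

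2. **Analysis.** State in SAP 6.2.1.2 and 6.2.1.3 that persistence titers taken after a nonstudy meningococcal vaccine are excluded from the Visit 6 and Visit 7 summaries for the affected serogroups, and report the number excluded at each visit. This fits the hypothetical strategy the SAP already names for these endpoints.

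The cost is one cell in each schedule copy, one procedure line, one SAP rule and, where Visit 7 is complete, one query per Group 1 participant. The recording page is already in use at other visits. No visit, endpoint or sample size changes.

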6.5.1. Prohibited During the Study

- Receipt of any blood products, including immunoglobulin, in the period 6 months before any blood draw.
- Nonstudy meningococcal vaccines.

- Nonlive or live nonstudy vaccines are not permitted 14 and 28 days, respectively, before or after any study vaccination.
- Intramuscular/sublingual allergen immunotherapy is not permitted within 14 days before or after any study vaccination.
- Systemic (oral, intravenous, or intramuscular) corticosteroid therapy within 28 days before or after any study vaccination.

6.5.2. Permitted During the Study

- Nonstudy vaccines used in the event of a disease outbreak or pandemic are allowed. In such situations, effort should be made to appropriately plan the administration of study intervention around dosing of the pandemic vaccine.
- Nonstudy vaccines (other than any meningococcal vaccines) that are part of recommended immunization schedules are allowed anytime during the study but should not be administered within 14 days (for nonlive vaccines) and 28 days (for live vaccines) before or after administration of study intervention.
- Antipyretic and other pain medication to treat symptoms following administration of study intervention is permitted.
- A local anesthetic may be used at the site of the blood draw.
- Topical antibiotics are permitted.
- Topical and inhaled corticosteroids are permitted.
- Hormonal contraceptives that meet the requirements of this study are allowed to be used in participants who are WOCBP (see [Appendix 4](#)).

6.5.3. Prior Treatments

If the participant is known to have ever received a PRP-OMP vaccine, the name of the vaccine and date of administration will be recorded on the CRF.

6.5.4. Prohibited Prior Treatments

Receipt of any blood products, including immunoglobulin, within 6 months before the first study vaccination.

6.6. Dose Modification

Not applicable.

6.7. Intervention After the End of the Study

No intervention will be provided to study participants at the end of the study.

7. DISCONTINUATION OF STUDY INTERVENTION AND PARTICIPANT DISCONTINUATION/WITHDRAWAL

7.1. Discontinuation of Study Intervention

In rare instances, it may be necessary for a participant to permanently discontinue study intervention (definitive discontinuation). Reasons for definitive discontinuation of study intervention include the following: AEs; parent(s)/legal guardian or participant request; protocol violation.

Note that discontinuation of study intervention does not represent withdrawal from the study. If study intervention is definitively discontinued, the participant will remain in the study to be evaluated for the collection of safety information. See the [SoA](#) and [Section 8.11.3](#) for data to be collected at the time of discontinuation of study intervention and follow-up for any further evaluations that need to be completed.

In the event of discontinuation of study intervention, it must be documented on the appropriate CRF/in the medical records whether the participant is discontinuing further receipt of study intervention or also from study procedures, posttreatment study follow-up, and/or future collection of additional information.

Premature termination of this study may occur because of a regulatory authority decision, change in the opinion of the IRB/EC, or study intervention safety problems, or at the discretion of Pfizer. In addition, Pfizer retains the right to discontinue development of MenABCWY at any time.

If a study is prematurely terminated, Pfizer will promptly notify the investigator. After notification, the investigator must contact the parent(s)/guardian of all participants and the hospital pharmacy (if applicable) immediately. As directed by Pfizer, all study materials must be collected and all CRFs completed to the greatest extent possible.

